5.2.9. BMI

The analysis set, analysis methodology and intercurrent events and missing data are the same as [Section 5.2.2](#).

5.2.10. Waist:chest circumference ratio

The analysis set, analysis methodology and intercurrent events and missing data are the same as [Section 5.2.2](#).

5.2.11. Population PK characterization in children aged ≥ 2 to < 11 years old with achondroplasia.

The analysis set for this endpoint will be the PK concentration set ([Section 3](#)); nonlinear mixed effect modeling will be performed to evaluate pharmacokinetic parameters. Additional details on the population PK modeling will be described in the population modeling analysis plan.

5.2.12. Rate of anti-drug antibodies

- Analysis set: FAS

Response rates of the development of anti-recifercept antibodies (ADA) and NAb. The percentage of subjects with positive ADA and NAb will be summarized by dose and cohort. For subjects with positive ADA or NAb, the magnitude (titer), time of onset and duration of ADA/NAb response will also be described, if data permit. The impact of ADA and NAb on PK and/or safety may also be assessed, if data permit. This may include:

- Spaghetti plots of individual intact and total recifercept concentration time profile, grouped by ADA/NAb status, produced separately by cohort.
- Table summaries of intact and total recifercept concentrations at visit and time by ADA and NAb status by cohort.

5.3. Other Endpoint(s)

5.3.1. CoIX

The analysis set, analysis methodology are the same as [Section 5.2.2](#), while intercurrent events and missing data follow methods detailed in [Section 4.3.1](#)

CCI [REDACTED]

[REDACTED]

[REDACTED]

[REDACTED]

[REDACTED]

[REDACTED]

[REDACTED]

[REDACTED]

5.4. Subset Analyses

Not applicable.

5.5. Baseline and Other Summaries and Analyses

5.5.1. Baseline Summaries

Demographics and baseline disease characteristics defined in [Section 2.4](#) will be summarized by treatment group according to Pfizer standards.

5.5.2. Study Conduct and Participant Disposition

Subjects evaluation, disposition, discontinuation will be summarized according to Pfizer standards. .

5.5.3. Study Treatment Exposure

The exposure to study drug will be summarized by total number of applications, the total number of days of dosing, the number and the proportion of participants who are compliant with the dosing regimen.

5.5.4. Concomitant Medications and Nondrug Treatments

Prior drug and non-drug treatment, concomitant drug and non-drug treatment will be summarized according to Pfizer standard.

5.5.5. Tanner Stage

Tanner stage and the change from baseline will be summarized at each visit by dose and gender.

5.6. Safety Summaries and Analyses

All safety analyses will be performed on the safety population and summarized in accordance with Pfizer Data Standards.

All clinical AEs, SAEs, TEAEs, withdrawal due to AEs, ECGs, vital signs and safety laboratory data will be reviewed and summarized on an ongoing basis during the study to evaluate the safety of participants.

Safety data will be summarized descriptively through appropriate data tabulations, descriptive statistics, categorical summaries, and graphical presentations, where appropriate. Categorical outcomes (eg, AEs) will be summarized by subject counts and percentage. Continuous outcome (eg, blood pressure, pulse rate, etc.) will be summarized using N, mean, median, standard deviation, etc. Change from baseline (CFB) in laboratory data, and vital signs will also be summarized. Participant listings will be produced for the safety endpoints accordingly.

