**Overall Design**

**Brief Summary**

This is a Phase 2 open label extension study to assess long-term safety, tolerability, PK, and efficacy of recifercept. The study will be offered to approximately 63 participants from the Phase 2 C4181005 study will be offered to participate who, in the opinion of the investigator, continue to have a positive risk: benefit profile. All enrolled participants will continue treatment with recifercept on 1 of 3 doses (1mg/kg QW, 2 mg/kg BIW, 1.5 mg/kg QD) for up to 24 months. Participants will be children diagnosed with achondroplasia aged  $\geq 15$  months to  $\leq 12$  years (inclusive); who have completed the C4181005 Phase 2 protocol.

Participants will continue to receive recifercept at the dose previously received in the Phase 2 study or at the therapeutic dose once this is identified.

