### 9.3.1. General Considerations

Data presented in tables will be summarized by recifercept dose (defined in [Section 4.1](#)) and total. If needed summary presentations may also be grouped by gender.

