2. ENDPOINTS AND BASELINE VARIABLES: DEFINITIONS AND CONVENTIONS

2.1. Primary Endpoint(s)

Safety

Safety and tolerability of recifercept as assessed through frequency and severity of AEs/SAEs.

Efficacy

Increase in height growth above expected in reference population [Merker et al, 2018].

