2.5.1. Adverse Events

Any events occurring following start of treatment or increasing in severity will be counted as treatment emergent.

Events that occur in a non-treatment period (for example, washout or follow-up) will be counted as treatment emergent and attributed to the previous treatment taken.

Any resolved AEs from study C4181005 will be reported as medical history. On-going AEs will be captured as ongoing with the start date from when they entered into the C4181008 study.

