4.2. General Methods

Data will be presented – ie, listed and summarized – by dose group, block and overall. Data summaries may also be grouped by gender. Continuous data will be summarized comprising mean, median, standard deviation, minimum and maximum. Categorical and binary data are summarized will be done via percentages.

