5.6.1. Adverse Events

Adverse events will be reported in accordance with the sponsor reporting standards.

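### The SAP has no rule for assigning adverse events after a dose switch and no person-time denominator, so by-dose AE percentages can mislead if children change dose

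*SAP*

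**What the plan says.** SAP 2.1 gives the primary safety endpoint as "Safety and tolerability of recifercept as assessed through frequency and severity of AEs/SAEs".

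On how it is summarized:

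- SAP 5.6: "Categorical outcomes (eg, AEs) will be summarized by subject counts and percentage".
- SAP 5.6.1 adds only: "Adverse events will be reported in accordance with the sponsor reporting standards".
- SAP 4.2: "Data will be presented – ie, listed and summarized – by dose group, block and overall". Protocol 9.3.1 agrees: "Data presented in tables will be summarized by recifercept dose".
- SAP 3 classes the safety set by the dose each child actually took, in the singular, and has no provision for a child who takes two.

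On dose changes:

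- The protocol synopsis has children continue "at the dose previously received in the Phase 2 study or at the therapeutic dose once this is identified". Protocol 4.3 repeats this.
- Protocol 6.5 allows step-down for tolerability, after which the child stays on the lower dose.
- Protocol 4.1 has each child enter on completing C4181005, so a single calendar switch date could fall at different study months for different children.

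On attribution and exposure:

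- SAP 2.5.1 says events in a non-treatment period "will be counted as treatment emergent and attributed to the previous treatment taken". It does not address a change from one active dose to another.
- SAP 5.5.3 reports "the total number of days of dosing" in a separate summary and does not link it to AE counts.
- SAP 5.1.1.1 does adjust the height model for whether a child has switched dose. The AE summary has no counterpart.

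**The concern.** Long-term safety of the doses and regimens is the first primary objective, and the by-dose AE and SAE tables are its main result. A percentage of children with an event rises with the time they are watched. If children leave some doses early and accumulate on another, the dose with more follow-up shows a higher percentage even when the risk is the same.

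The alternative is to keep each switched child under a single dose. Events that occurred on the other dose are then counted in the wrong column. The SAP does not choose between these two ways of counting, and each can mislead a reader who compares doses.

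**Working it through.** The plan states no AE rate, safety power or hypothesis, so there is no planned figure to reproduce. The check asks what the planned percentages show when the true risk is the same on every dose.

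**Inputs from the documents.** Three doses, about 63 children, treatment for up to 24 months (Protocol 1.1 and 4.1).

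**Assumptions.** A constant AE hazard, equal on all doses, from 0.1 to 5 per child-year; switch times as shown below; 21 children per dose (63/3). The early Phase 2 data in Protocol 2.2.1 give event counts without exposure time, so no rate can be derived from them.

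**Formula.** P(at least one event in T months) = 1 − exp(−rate × T/12).

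**Reading 1: a switched child counts under each dose.** At 0.5 per child-year:

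- 6 months: 1 − exp(−0.25) = 22.1%
- 18 months: 1 − exp(−0.75) = 52.8%
- 24 months: 1 − exp(−1.0) = 63.2%

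| Rate per child-year | 6 months | 18 months | Ratio |
|---|---|---|---|
| 0.1 | 4.9% | 13.9% | 2.86 |
| 0.25 | 11.8% | 31.3% | 2.66 |
| 0.5 | 22.1% | 52.8% | 2.39 |
| 1 | 39.3% | 77.7% | 1.97 |
| 2 | 63.2% | 95.0% | 1.50 |
| 5 | 91.8% | 99.9% | 1.09 |

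The split of time matters as much as the rate. At 0.5 per child-year, 3 versus 21 months gives 11.8% versus 58.3%, 9 versus 15 months gives 31.3% versus 46.5%, and 12 versus 12 months gives 39.3% on both.

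At trial level, suppose two dose groups switch to the third at month 6. The third dose then holds its own children for 24 months and the two incoming groups for 18. Its percentage is (63.2 + 2 × 52.8)/3 = 56.3%. The table shows about 22/22/56% for three doses of equal risk.

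A simulation (21 children per dose, two groups switching to the third at uniformly spread times, 1,500 runs per scenario, rate 0.5) gave:

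| Switch window | Crude percentages | Events per child-year |
|---|---|---|
| Months 0–12 | 21/21/56% | 0.49/0.49/0.50 |
| Months 6–18 | 38/39/47% | 0.50/0.50/0.50 |

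Dividing events by time on dose recovers the equal risk in both cases. With no switching and full follow-up, every dose shows 63.2% and nothing is distorted.

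**Reading 2: a switched child counts under one dose.** With a constant hazard, the share of events in the wrong column equals the share of time on the other dose. For a switch at month 6 of 24, that is 18/24 = 75% of expected events if the child stays under the initial dose, or 6/24 = 25% if moved to the later one. With equal hazards and full follow-up the percentages still agree across doses. The harm here arises when hazards differ, because the tables then blend them.

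**The case against.** The strongest case against is that the problem may never arise. Switching depends on a therapeutic dose being identified, for which no date is given, and step-down is for individual children. A reader might infer that unequal time on dose is built into the design. The documents support only that it is permitted and that the SAP anticipates it in the height model. This stands, and it makes the size conditional.

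Second, SAP 3 may mean one dose per child. That also stands as a possible reading. It changes the form of the defect without removing it.

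Third, SAP 5.6 and 5.6.1 defer to sponsor standards that are not reproduced, and 5.6 also plans graphs and listings. The standards may contain exposure-adjusted rates or an attribution rule, so one cannot say that percentages are all that will be produced. But the SAP does not commit to either, and the measure it does name for AEs is counts and percentages.

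Fourth, the study tests no hypotheses (SAP 4.1). That removes concern about error rates, but the by-dose description is itself the primary safety result.

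Fifth, a reader might argue that injection site reactions have a second biased denominator, because daily dosing means more injections than weekly dosing. The documents do not support this. The objective covers dosing regimens, and injection frequency is part of the regimen. More reactions per child on a daily schedule would be a real tolerability difference.

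**Conclusion.** The gap is real: a primary endpoint is summarized by dose with no rule for events after a switch between doses and no person-time denominator. The SAP should be changed. How much it would distort the tables cannot be known from the documents.

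Under a constant, equal hazard of 0.5 per child-year, and with switched children counted under each dose, 6 versus 18 months on dose gives 22% versus 53%, and a month-6 switch of two groups gives about 22/22/56%. The effect is modest for switches around mid-study (38/39/47%), absent for a 12/12 split, and negligible if few children switch or if events are near-universal.

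Three stronger readings should be avoided:

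- A reader might contrast 6 with 24 months (22% versus 63%). One child cannot have both months on one dose and 24 on another within the planned 24 months, and a dose that receives switchers mixes 18- and 24-month follow-up, which gives 56%.
- A reader might infer that the tables will rank the doses wrongly. The equal-hazard calculation shows a spurious gap. A reversed order would also need the true hazards to differ, and the documents give no hazards.
- A reader might infer that the person-time is already derived. Days of dosing in SAP 5.5.3 may mean injection days, which for weekly dosing is not time at risk, and they are not split by dose for a child who switches.

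**What to change.** In SAP 5.6 and 5.6.1:

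1. Assign each treatment-emergent AE to the dose in use at onset, and extend the SAP 2.5.1 rule to cover a change between doses.
2. Beside the planned percentages, report for each dose: person-years on that dose, number of events, children with an event, and the exposure-adjusted incidence rate with its 95% CI. Take person-years from the intervention start and stop dates recorded under Protocol 6.4, not from injection days. Confirm that the CRF dates every dose change, including a move to the therapeutic dose.
3. Also show percentages by C4181005-assigned dose, using the randomized set already defined in SAP 3. Keep the dose-received tables, so that the safety set in Protocol 9.2 is unchanged.
4. Add a summary censored at each child's first dose change. Rates alone do not remove the selection that arises when children step down because they did not tolerate a dose.
5. Optionally, add a per-injection rate for injection site reactions as a supplement to the per-child figures, not as a correction of them.

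The cost is SAP wording and one extra set of tables. No new data collection is foreseen, subject to the CRF check in item 2.

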5.6.1. Adverse Events

Adverse events will be reported in accordance with the sponsor reporting standards.

5.6.2. Laboratory Data

Laboratory data will be listed and summarized by treatment in accordance with the sponsor reporting standards. Baseline is defined as the last visit prior to Day 1.

5.6.3. Vital Signs

Absolute values and changes from baseline in supine systolic and diastolic blood pressure, oral temperature, and pulse rate will be summarized by treatment in accordance with the sponsor reporting standards. Tables will be paged by parameter. Baseline is as defined in [Section 2.4](#).

Mean changes from baseline for supine systolic and diastolic blood pressure, oral temperature, and pulse rate for each treatment will be plotted against time post-dose. On each plot there will be 1 line for each treatment. Corresponding individual plots of changes from baseline will also be produced for each treatment.

Maximum absolute values and changes from baseline for vital signs will also be summarized descriptively by treatment, using categories as defined in [Appendix 5](#). Numbers and percentages of subjects meeting the categorical criteria will be provided. All planned and unplanned post-dose timepoints will be counted in these categorical summaries. All values meeting the criteria of potential clinical concern will be listed.

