1.1. Study Objectives, Endpoints, and Estimands

Objectives	Estimands	Endpoints
Primary:	Primary:	Primary:

 Evaluate the long-term safety and tolerability of recifercept doses and dosing regimes in participants aged ≥ 15 m to < 12 years with achondroplasia. 	N/A.	Long-term Safety and tolerability of recifercept as assessed through frequency and severity of AEs/SAEs.

 To assess long-term efficacy of recifercept to increase height growth in children with achondroplasia. 	
 The primary efficacy estimand is intended to provide a population level estimate of the effect of the IP on a continuous endpoint. 
Population-level summary: ratio between participants in the trial and a reference population [Merker et al, 2018]¹ in growth of height at 24 month; ratio between treated and reference population is observed change-from-baseline of treated participants standardized by reference participant given age and gender.
	
 Increase in height growth above expected in reference population [Merker et al, 2018].¹
Secondary:	Secondary:	Secondary:

 To evaluate the PK of recifercept in children aged ≥ 15m to ≤ 12 years old with achondroplasia. 		Population PK characterization in children aged ≥ 15 m to < 12 years old with achondroplasia. CL/F and other PK parameters of recifercept to assess exposures in different age group.

Objectives	Estimands	Endpoints

 To assess efficacy of recifercept to improve achondroplasia-related complications. 		
 Sitting height/standing height ratio. Arm span to height/length difference. Knee height:lower segment ratio. Occipito-frontal circumference. Ratio of occipito-frontal distance to occipito-mid-face measurements. z-score of the above proportionality and skull morphology where achondroplasia reference datasets exist (occipito-frontal circumference, arm span, sitting height). Fixed flexion angles at elbow. Polysomnography parameters in those with pre-existing sleep-disordered breathing at the time of enrollment. BMI. Waist:chest circumference ratio.

 Assess change in individual safety parameters. 		
 Change from baseline in safety labs, vital signs, physical examination. Rate of ADAs.

CCI [REDACTED]
	
[REDACTED]
	
[REDACTED]

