1.2. Study Design

This is a Phase 2 open label extension study to assess the long-term safety, tolerability, PK and efficacy of recifercept.

Approximately 63 children from the Phase 2 C4181005 study will be offered to participate who, in the opinion of the investigator, continue to have a positive risk:benefit profile. Participants will be children diagnosed with achondroplasia aged $\geq 15\text{m}$ - ≤ 12 years (inclusive). All participants will continue to receive 1 of 3 doses of recifercept (1 mg/kg QW, 2 mg/kg BIW or 1.5 mg/kg QD) until a therapeutic dose is identified for up to 24 months.

Enrollment of participants will follow their completion of the C4181005 Phase 2 study and only be offered to those who, in the opinion of the investigator, continue to have a positive risk: benefit profile. PK and immunogenicity samples will be collected to assess long-term safety of recifercept.

Once a final therapeutic dose has been identified, the Pfizer IRC may decide to extend the study treatment duration and data collection (including final adult height) period beyond 24 months. Any significant changes to the protocol will be made via substantial protocol amendment.

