2.4. Baseline Variables

The following baseline variables will be summarized for each treatment group (per [Section 3](#)). Details of summary analyses are described in [Section 5.5.1](#).

Demographic characteristics:

- Baseline age
- Gender (female vs. male);
- Race (white, black, Asian, other);
- Baseline body weight;
- Baseline height (cm);
- Baseline Body Mass.

The baseline data measured at Day 1 are:

- Vital signs
- Physical Examinations

The following variables are to have their baseline value defined as latest screening result relative to Day 1:

- Medical history & demography, Height/Weight.
- Neurological Examinations
- Vital Signs/Physical Examinations with missing Day 1 values

Where Day 1 result is missing, baseline data will be defined as the latest result from C4181005 prior to enrollment, where available.

Medical history and concomitant medications ongoing from the C4181005 study will be reentered in C4181008 with the start date from when they entered into the C4181008 study.

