4.1. Hypotheses and Decision Rules

There are no statistical hypotheses for this protocol.

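### SAP Appendix 5 applies one set of absolute vital-sign limits from about 18 months to 14 years, so its counts of clinical concern depend partly on age (minor)

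*SAP*

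**What the plan says.** SAP 5.6.3 sets up a categorical summary of vital signs and points to Appendix 5 for its limits: "Maximum absolute values and changes from baseline for vital signs will also be summarized descriptively by treatment, using categories as defined in". Each child who meets a category is counted, with a percentage, and the values that meet one are listed. On timing it adds: "All planned and unplanned post-dose timepoints will be counted in these categorical summaries". One reading beyond a limit is therefore enough to count a child.

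Appendix 5 contains:
- absolute limits for systolic pressure (below 90), diastolic pressure (below 50) and supine pulse (below 40 or above 120);
- change-from-baseline rows for systolic and diastolic pressure, printed with ≤ 30 and ≤ 20;
- no change-from-baseline row for pulse;
- no age band, percentile or z-score in any row.

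The SAP 1.1 safety objective covers long-term safety "in participants aged ≥ 15 m to < 12 years with achondroplasia". SAP 1.2 and Protocol 5.1 put the upper entry age at 12 years inclusive, a difference that does not matter here. Treatment continues "until a therapeutic dose is identified for up to 24 months". The Protocol 1.3 schedule has vital signs at M3, M6, M9, M12, M15, M18, M21 and M24, and none at Enrollment.

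No age split of the table is stated. SAP 4.2 presents data "by dose group, block and overall", with gender as an option. SAP 5.4 on subset analyses reads "Not applicable".

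**The concern.** A fixed limit means different things at different ages when the normal range moves. With blood pressure rising and pulse falling as children grow, four effects follow:

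1. Low systolic and diastolic flags are raised more often in the youngest.
2. Pulse above 120 is also raised more often in the youngest.
3. Pulse below 40 can miss a pulse that is abnormally low for a toddler.
4. Pulse above 120 can miss a pulse that is abnormally high for a young adolescent.

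Evaluating long-term safety is a primary objective, and change from baseline in vital signs is a named secondary safety endpoint. This table is the SAP's categorical screen for vital signs of clinical concern. At stake is whether its counts mean what their label says.

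**Working it through.** The plan states no expected flag rate, so there is no figure to reproduce. The check has a structural part from the documents and an illustration from assumed values.

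**From the documents**
- Youngest possible child: 15 + 3 = 18 months at M3 and 15 + 24 = 39 months at M24.
- Oldest possible child: 12 years + 24 months, about 14 years at M24.
- Scheduled readings: 8. Unscheduled readings also count and can only raise the chance of a flag.

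**Assumed, because the documents give none**
- Systolic mean: youngest 85-100, oldest 105-115; SD 8-10.
- Pulse mean: youngest 100-120, oldest 70-90; SD 12-15.
- Within-child correlation r = 0.5, varied from 0.3 to 0.7.
- Growth drift from M3 to M24 in the youngest: systolic +5 mm Hg, pulse −10/min. None in the oldest.
- Normal readings and no drug effect.

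**Single visit, systolic below 90.** P = Φ((90 − mean)/SD).
- Youngest: Φ((90 − 100)/8) = Φ(−1.25) = 11%, up to Φ((90 − 85)/8) = Φ(0.625) = 73%.
- Oldest: Φ((90 − 115)/8) = Φ(−3.125) = 0.1%, up to Φ((90 − 105)/10) = Φ(−1.5) = 7%.

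**At least one flag in 8 visits.** Simulated for 400,000 children as y = mean + drift·t + SD·(√r·u + √(1 − r)·e). Here t runs from 0 at M3 to 1 at M24, u is one standard normal draw per child and e one per visit. A child is flagged if any visit is beyond the limit.

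| Limit and setting | Youngest | Oldest (no drift) |
|---|---|---|
| Systolic <90, no drift, r = 0.5 | 38%-98% | 0.6%-27% |
| Systolic <90, drift +5 in youngest, r = 0.5 | 27%-95% | 0.6%-27% |
| Systolic <90, drift +5 in youngest, r = 0.3-0.7 | 21%-98% | 0.5%-33% |
| Pulse >120, drift −10 in youngest, r = 0.5 | 12%-81% | <0.1%-12% |

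The outer ranges meet or overlap, so the fair test holds the SD equal. The smallest systolic contrast (means 100 and 105, drift in the youngest only, r = 0.5) gives 27% against 15% at SD 8, and 40% against 27% at SD 10. The direction holds, but the gap may be modest.

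**Pulse sensitivity.** z = (value − mean)/SD.
- Oldest, 115/min: (115 − 90)/15 = 1.7 to (115 − 70)/12 = 3.8 SD above the mean, not flagged.
- Youngest, 60/min: (60 − 100)/15 = −2.7 to (60 − 120)/12 = −5.0, that is 2.7 to 5.0 SD below the mean, not flagged.
- Youngest, the limit of 40 itself: (40 − 100)/15 = −4.0 to (40 − 120)/12 = −6.7. The flag is close to inert at that age.

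**Diastolic below 50.** The direction is the same as for systolic. No size is offered.

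**Change rows.** Read literally, a category of decrease or increase ≤ 30 (or ≤ 20) captures small changes and leaves out large ones. It may be a slip in the sign or an effect of text extraction. Either way, as printed the rows cannot be relied on to offset the age problem for blood pressure.

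**The case against.** The strongest reply is that little depends on this table. SAP 4.1 states: "There are no statistical hypotheses for this protocol". No decision rule in the documents uses the flags. Protocol 8.2.3 has an abnormal blood pressure repeated after one minute, clinically significant vital signs become adverse events on the investigator's judgement, and SAP 5.6 has vital signs reviewed throughout the study. This stands, and it sets the severity.

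A reader might infer that an unflagged abnormal pulse disappears from the report, because pulse has no change category. The documents do not support that. SAP 5.6.3 summarises pulse changes, plots their means and produces individual change plots, and SAP 5.6 promises participant listings for the safety endpoints. A pulse of 60 in a toddler would be absent from the flag count and the flagged-value listing, but not from the reported data. These outputs let a reader look behind a count; they do not correct it.

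It can also be said that age separation may already be planned, since SAP 4.2 mentions a block and SAP 5.2.12 a cohort. Neither term is defined in these documents. An age meaning is possible but cannot be assumed.

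The sponsor reporting standards cited in SAP 5.6.3 might be age-specific, but they are cited there for the absolute-value and change summaries. The categorical table is tied to Appendix 5.

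Finally, the percentages come from assumed norms in which the age gradient is an input. That is fair. The age trend alone gives the direction. How many ordinary readings fall beyond each limit needs norms that the documents do not contain.

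**Conclusion.** The point holds as a minor one. The single set of limits, the any-reading rule and the wide age range are all read directly from the documents. Given only that resting blood pressure rises and pulse falls with age, the categorical counts and flagged-value listing are distorted by age in the four directions described.

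The size is not established. Every mean, SD, correlation and drift above is an assumption, and the comparison is between the age extremes. The documents do not say how many of the approximately 63 children are near either end.

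A reader might also infer that the dose comparison is biased. That is not shown: it would need the ages to differ between dose groups, and the documents give no age distribution by dose. The effect is limited to the interpretation of one descriptive safety table, with adverse event reporting and ongoing safety review running alongside.

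**What to change.** In Appendix 5, replace the absolute limits with age-specific limits (sex-specific too for blood pressure) or z-scores, taken from a paediatric reference named in the SAP before analysis. Add age at visit to the listing of flagged values. Check the direction of the ≤ signs in the blood pressure change rows at the same time.

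If no reference suits achondroplasia, keep the limits but tabulate flags overall by a few broad age bands at the visit, for example under 3, 3 to under 8, and 8 years or older. Age bands alone do not restore sensitivity for pulse, so a pulse change-from-baseline category could be added. It should be read by age band, because a fixed change is itself age-dependent. It also needs a baseline. With no vital signs scheduled at Enrollment, that falls to the rule in SAP 2.4: "Where Day 1 result is missing, baseline data will be defined as the latest result from C4181005 prior to enrollment, where available".

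The cost is SAP wording and a lookup table in programming. Birth month and year are already required by Protocol 8, and gender is a baseline variable in SAP 2.4. There are two downsides. A paediatric reference may not be specific to achondroplasia. Splitting three bands by three doses leaves about 63/9 = 7 children per cell on average, which is why the bands are best shown overall.
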